#### **7.2.4 Day of Surgery -Operating Room**

Once in the operating room, general anesthesia will be induced according to the standard of care for the patient and surgery. The ESPB pump will continue to deliver automatic boluses of 15ml of either study medication or normal saline every 3 hours throughout the duration of surgery. Intraoperatively, anesthesia is required to use only Fentanyl, a short acting opioid, for additional pain control and requested to refrain from using hydromorphone or morphine. At the completion of the case, Ondansetron will be administered for postoperative nausea.

Dexamethasone will not be routinely administered as this can also have analgesic effects. All medications administered by the anesthesia team during the operative case will be recorded in the anesthesia record and reviewed and documented by a member of the research team.

#### **7.2.5 Postoperative hospital stay**

As per standard of care, the patient will be taken to the post anesthesia care unit (PACU). Here, [name] will be present to ensure the PACU team for the study patient are sufficiently educated on the protocol requirements and to ensure safety and protocol adherence. The ESPB pump will be delivering the automatic boluses of study drug (15ml every 3 hours) and additionally allow the patient to self-administer an on demand dose of study drug (0.2% Ropivacaine vs. normal saline) 5ml every 30 minutes throughout their hospital stay. The pump will permanently lock out and cease administration of both the automatic and self-administered boluses if the total dose of study drug reaches 770mg. The patient will still be able to initiate a demand dose, but no medication will be provided. If a lock out occurs prior to POD3, when the pump is scheduled to be removed, it will remain in place until the schedule day of removal. In the PACU, if the patient has additional pain requirements beyond the patient's previously determined acceptable pain score (asked pre-operatively per hospital standard) the PACU team may start a patient controlled analgesia (PCA) containing a set demand dose of hydromorphone 0.2mg every 6 mins. The pump will lock out if the maximum dose of 2mg per hour is reached. Bolus IV dosing of hydromorphone may be administered at the start of the PCA and throughout the hospital stay if deemed necessary by the treating physician team to control patient pain needs. One gram of acetaminophen IV every 8hrs will also be started in the PACU and continued through the patient's hospital stay. Acetaminophen will be converted over to oral regimen on POD 1. When transferred to the inpatient wards, [name] will ensure the nurse assigned to the study patient is aware and properly educated on the protocol requirements on a daily basis. She will also monitor for subject safety and protocol adherence while the study patient remains in the hospital by both identifying the patient room as on a research study as well as through daily interaction with the nursing team. While on the inpatient wards, additional pain control adjuncts will be provided using oral oxycodone 5-10mg every 4 hours administered based on a pain scale: pain 3-6 translates to 5mg tab and pain 7-10 translates to a 10mg tab. The PCA, as outlined above, may be started later in the hospital course, if needed, based on the patient's needs. The ESP block will be discontinued between 6AM-9AM on POD 3. Specific research order sets for this study will be created by the principal investigator for use of the study drug/placebo, narcotics and acetaminophen. All medications and dosages administered during the hospital stay (PACU and inpatient ward) will be reviewed and documented by a member of the research team to tabulate the total IV and oral opioid and study drug requirement of all study patients. Daily pain scales using the Visual analogue scale (VAS) 0-10 will be provided to the patient by a member of the research team, each morning between 9AM-12PM, on POD 1, 2 and 3 (scale attached). Additionally, on POD 1, between 9AM-12PM, a brief patient satisfaction survey (which has been previously validated (11)) will be provided to the patient to complete by a member of the research team (document attached).

On day of discharge, the same brief patient satisfaction survey will be provided again for the patient to complete prior to leaving the hospital. Each patient will be provided with a standard home pain regimen which will include use of acetaminophen 500mg oral tabs every 6 hours as needed, oxycodone 5mg oral tabs every 4 hours as needed with a quantity of 30 tabs dispensed.

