### 1.3 Secondary Study Endpoints

1. Pain scores using the Visual analogue scale (VAS) 0-10 on postoperative day (POD) 2 and 3.
2. Total dose of IV and oral opiate and study drug use at the completion of POD 1, 2 and 3.
3. Length of hospital stay
4. Patient satisfaction survey of pain control given on POD 1, at discharge and at time of postoperative visit (within 14 days of discharge)—(survey document attached)
5. Amount of oral opiates used from discharge to postoperative visit
6. Total cost of hospital stay

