### **8.3 Statistical methods**

For the primary endpoint, a 2-sided t-test will be used. T-tests will also be used for all secondary endpoints, unless the assumption of normality does not hold, in which case a Wilcoxon Rank Sum Test will be used.

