### **10.4 Frequency of data collection**

Data will be collected via the electronic medical record and begin following patient randomization. Total IV and oral opiate during the hospitalization will be collected post discharge. The VAS pain scales will be administered between 9AM-12AM on POD 1, 2 and 3 and collected daily. The patient satisfaction

survey will be collected on POD 1, day of discharge and at the telephone post operative visit, within 14 days from discharge.

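### The POD 3 pain score, a secondary endpoint, is scheduled 0-6 h after the block is stopped, so it does not measure pain on the block; separately, two sections disagree on the starting bolus strength.

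*Combined protocol and SAP*

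**What the plan says.** **Timing.** Section 7.2.5 fixes both clock windows. For the block: "The ESP block will be discontinued between 6AM-9AM on POD 3". For the pain score: "each morning between 9AM-12PM, on POD 1, 2 and 3". Section 10.4 repeats the scoring schedule with a different closing time: "The VAS pain scales will be administered between 9AM-12AM on POD 1, 2 and 3 and collected daily". The 12AM there is probably a slip for 12PM.

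Until removal the pump gives automatic boluses every 3 hours, and section 7.2.5 also allows an "on demand dose of study drug (0.2% Ropivacaine vs. normal saline) 5ml every 30 minutes throughout their hospital stay". Delivery can end before removal only if the dose limit is reached.

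**Endpoint and analysis.** Section 1.2 makes POD 1 pain the primary endpoint. Section 1.3 lists as one secondary endpoint: "Pain scores using the Visual analogue scale (VAS) 0-10 on postoperative day (POD) 2 and 3". Section 8.3 says "T-tests will also be used for all secondary endpoints", with a rank-sum test if normality fails. Neither section treats POD 3 differently from POD 2 or mentions whether the block is running.

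**Starting bolus.** Section 7.2.3 orders 20 ml of ropivacaine 0.5% through the catheter. Section 7.4.6.3 says that the syringe holds the initial bolus, and that in the active arm both syringe and cartridge contain ropivacaine 0.2%. The regimen table in section 7.4.2 also lists only 0.2%.

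**The concern.** The trial asks whether the block improves pain after surgery. A reader of sections 1.2 and 1.3 would take the scores on POD 1, 2 and 3 as three looks at the same thing: pain with the block running against pain with a sham block running. The schedule makes the third look different in kind, because by then the block has been stopped in both arms.

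What is at stake is how the POD 3 result can be read. If the arms differ, the finding is about pain shortly after removal. If they do not, the plan gives no way to tell whether the block had stopped helping by POD 3 or had merely been switched off beforehand. The protocol collects no POD 3 score that would separate the two.

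The bolus conflict is a separate matter. Clinicians following section 7.2.3 and pharmacists following section 7.4.6.3 would be working to different doses for the same syringe.

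**Working it through.** The plan gives no figure of its own on this point. Its one statistical figure, 17 per group in section 8.2, concerns pain scores with a 2-point difference and SD 2. An exact two-sided t-test at 0.05 needs 16.7, so 17 per group, with 80.7% power. That figure reproduces, and the timing below does not enter it.

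**Stop-to-score gap on POD 3**

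Inputs, all from section 7.2.5: stop between 06:00 and 09:00; score between 09:00 and 12:00.

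- Shortest gap = earliest score minus latest stop = 09:00 - 09:00 = 0 h.
- Longest gap = latest score minus earliest stop = 12:00 - 06:00 = 6 h.
- The two windows meet only at 09:00, so no on-schedule POD 3 score precedes the stop.
- If both times are spread evenly over their windows (an assumption), the mean gap is the difference of midpoints: 10:30 - 07:30 = 3 h.

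Reading the closing time in section 10.4 literally as midnight, the longest gap becomes 24:00 - 06:00 = 18 h. The window still opens at 09:00, so the conclusion does not change.

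**The same comparison on POD 1 and POD 2**

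- POD 2: the score window closes at 12:00, which is 18 h before a 06:00 stop and 21 h before a 09:00 stop on POD 3.
- POD 1: one day earlier, so 18 + 24 = 42 h to 21 + 24 = 45 h before the stop.

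Both windows lie wholly inside the period when the pump is scheduled to run.

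**Starting bolus**

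Inputs: 20 ml (section 7.2.3); 0.5% = 5 mg/ml (section 7.2.3); 0.2% = 2 mg/ml (section 7.4.6.3).

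- Section 7.2.3: 20 ml x 5 mg/ml = 100 mg.
- Section 7.4.6.3, at the same volume: 20 ml x 2 mg/ml = 40 mg.
- Difference = 100 - 40 = 60 mg; ratio = 100 / 40 = 2.5.

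Section 7.4.6.3 states no volume, so the 40 mg takes its 20 ml from section 7.2.3.

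**The case against.** The strongest reply is that nothing is broken. Section 1.3 defines the endpoint by day, not by whether the block is running. One clock window serves all three days. The stop window closes just as the score window opens, which fits a deliberate sequence. Both randomised arms are scored on the same schedule, so the POD 3 comparison is fair for pain that morning, and section 8.3 plans no comparison of POD 3 with earlier days. On this view the choice between on-block and just-off-block pain is a choice of estimand, and at most a label is missing.

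Much of that stands. A reader might infer that the POD 3 comparison is biased; it is not. What does not stand is that the choice has been made: no section says that POD 3 pain is an after-removal measure, and it shares an endpoint with POD 2 pain, which is not. A label alone would make the text clear, but would still leave the trial without an on-block score on POD 3.

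Two stronger readings are tempting and should be resisted.

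- **That the stop dilutes the POD 3 effect by a known or likely amount.** This needs the duration of effect after the last ropivacaine dose, which the documents do not give. Some effect may persist through the scoring window.
- **That the dose limit also spoils the POD 3 total of study drug use.** Section 1.3 includes "Total dose of IV and oral opiate and study drug use at the completion of POD 1, 2 and 3", and section 7.2.5 has the pump "permanently lock out and cease administration of both the automatic and self-administered boluses if the total dose of study drug reaches 770mg". How much room this leaves for demand doses depends on when the block starts, whether the starting bolus counts toward the limit, and whether a bolus that would pass the limit is withheld. The text settles none of these. Analysing demand attempts instead would need pump logging that is not described.

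**Conclusion.** The point holds in a limited form. On schedule, every POD 3 pain score is taken 0-6 h after the block is stopped, and POD 1 and POD 2 scores are taken with the pump still scheduled to run. The 0-6 h range rests only on the two windows in section 7.2.5. The POD 3 result answers a question about pain after removal, and a null result there would not show that the block had no benefit while running.

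Three limits apply. The claim covers on-schedule scores: section 3.1 requires a planned stay of only 24 hours, so some patients may have left before POD 3. In a patient whose pump has locked out, drug delivery ended before the formal stop. And the effect on the VAS scale cannot be calculated from the documents.

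The timing affects one time point of a secondary endpoint. It does not affect the primary POD 1 score or the sample size.

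The bolus conflict is real and independent of the timing: 100 mg against 40 mg for the same step in the active arm. The documents do not show which is intended.

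**What to change.** 1. In section 7.2.5, add a VAS immediately before the block is stopped on POD 3. In section 1.3, name it as the on-block POD 3 score. Keep the existing 9AM-12PM score and label it 'after removal'. Correct the closing time in section 10.4 to match section 7.2.5 if 12PM is meant.
2. Have the investigator confirm the intended strength of the starting bolus, and correct whichever of sections 7.2.3 and 7.4.6.3 is wrong, so that pharmacy prepares the dose the procedure orders. If 0.5% is intended, section 7.4.2 should show it as well.

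The cost is protocol wording plus one extra VAS per patient, with a team member present at removal. The added score falls at 6-9 AM, earlier than the scores on POD 1 and POD 2; keeping the later score preserves a same-clock-time measure. For a patient already locked out, the added score is before removal but not on drug, and should be reported as such. The dose limit and removal time need not change.

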#### **7.2.6 Postoperative clinic visit**

Due to the COVID pandemic, a member of the research team will perform a telephone visit at 14 days postoperatively to determine and document the number of oral oxycodone tablets remaining out of a total of 30 tabs dispensed. Additionally, this member of the research team will also have the study patient fill out the same brief patient satisfaction survey (document attached). It is at this time that the patient's participation in this study will be concluded.

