### **3.3.2 Follow-up for withdrawn subjects**

If subjects need to be withdrawn from the study based on the above reasons, they will transition to following the clinical standard of care that is medically required for their particular situation. The block that is in place will be unblinded to the physician and patient. Unblinding will help the physician and patient understand if it may be worth trying to continue with the block in such circumstances as a means of pain control. Continuation with the blinding procedures could only delay achievement of adequate pain control and removal of unnecessary hardware, if the block ends up containing the control—normal saline. The remainder of the hospital course for these withdrawn subjects will continue according to standard medical practice. Their course will continue to be tracked for research purposes and they will be included and reported in the study results.

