### **7.3 Duration of Participation**

The patient will remain in the study until their telephone postoperative visit occurring within 14 days from discharge from the hospital.

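### Home opioid use is measured only as oxycodone tablets gone from the first 30, so any refill or other oral opioid a patient obtains would go unrecorded

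*Combined protocol and SAP*

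**What the plan says.** Section 1.3 lists as the fifth secondary endpoint: "Amount of oral opiates used from discharge to postoperative visit". The wording is not limited to one drug or one prescription.

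Section 7.2.5 sets the discharge supply: "oxycodone 5mg oral tabs every 4 hours as needed with a quantity of 30 tabs dispensed". Section 7.2.6 then has a team member establish by telephone the "number of oral oxycodone tablets remaining out of a total of 30 tabs dispensed". Use is evidently meant to be 30 minus that number. No question about refills, a second prescription or another opioid is described.

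The other statements about collecting opioid data stop at discharge. The medication review in Section 7.2.5 covers the recovery unit and the ward. Section 10.4 says: "Total IV and oral opiate during the hospitalization will be collected post discharge". The same section names a general source, "Data will be collected via the electronic medical record and begin following patient randomization", but does not mention prescriptions after discharge.

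The end of the counting period is given in two ways. Section 7.2.6 says the team will "perform a telephone visit at 14 days postoperatively". Section 7.3 refers to a "telephone postoperative visit occurring within 14 days from discharge from the hospital", and Sections 1.3 (item 4) and 10.4 also count from discharge.

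Section 8.3 plans t-tests for secondary endpoints, with a Wilcoxon rank sum test where normality fails.

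**The concern.** The endpoint and its measurement do not match. The endpoint is total oral opioid; the measurement is one drug from one fill. A patient who empties the bottle and stops, and a patient who empties it and then obtains more, are both recorded as 30 tablets. Their true use differs, and nothing else in the plan separates them.

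This matters because reducing opioid use is the stated rationale of the trial (Section 2.3), and this is the only endpoint that measures opioid use after the patient goes home. Unrecorded use can occur only among patients who obtain opioid beyond the counted tablets. If the block reduces home opioid need, such patients would more often be controls, and the comparison would lean towards no difference.

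Withdrawn patients add to the problem. They include those whose pain exceeds every option in the protocol (Section 3.3.1, item 7). Section 3.3.2 moves them to standard care but keeps them in the results: "Their course will continue to be tracked for research purposes and they will be included and reported in the study results". The protocol does not say whether their discharge supply is still the standard 30 tablets, so a count out of 30 may not describe their use.

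**Working it through.** The documents give no expected home use, refill policy, power statement or target difference for this endpoint, so there is no plan figure to reproduce. The stated sample size belongs to the primary endpoint and does not depend on this measurement.

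**1. Ceiling on recorded use.** Recorded use = 30 − tablets remaining. The most it can be is 30 − 0 = 30 tablets, or 30 × 5 mg = 150 mg oxycodone.

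**2. Time to reach the ceiling.** One tablet every 4 hours is at most 24 / 4 = 6 tablets a day, and 30 / 6 = 5 days.

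**3. Length of the counting window.**

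| Reading | Days at home | Maximum at written frequency | Ceiling as share of maximum | Average daily use that empties the supply |
|---|---|---|---|---|
| Up to 14 days from discharge (upper limit) | 14 | 14 × 6 = 84 | 30 / 84 = 36% | 30 / 14 = 2.1 |
| 14 days after surgery, assuming a 3-day stay | 14 − 3 = 11 | 11 × 6 = 66 | 30 / 66 = 45% | 30 / 11 = 2.7 |

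The 3-day stay is an assumption. The reading that counts from discharge has no lower limit, so the window could also be shorter than either row. The table shows that the supply can run out inside the window. It does not show that it will.

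**4. Effect on the difference in means.** Let E be the mean number of unrecorded tablets per patient in an arm. The control-minus-block difference is understated by E(control) − E(block).

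- No patient obtains more opioid: 0 − 0 = 0 tablets.
- Extra use is equal in both arms: E − E = 0 tablets. Use is under-recorded in each arm, but the difference is not biased.
- 2 of 20 controls and no block patients take 20 more tablets each (assumption): (2 × 20) / 20 − 0 = 2 tablets per patient, or 2 × 5 = 10 mg.

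The formula is symmetric: if the extra use fell mainly in the block arm, the difference would be overstated.

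**5. Effect on the rank test.** In the third scenario, suppose the two controls are recorded at 30 instead of 50 and no block patient is at 30. Their order against every block patient is unchanged, and so is the rank sum. The rank comparison is affected only when capped controls are tied with block patients who also used 30. Ranks limit the damage in the first case but cannot recover use that was never recorded.

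**The case against.** The strongest reply is that the endpoint concerns opioid used, not opioid needed. Every patient who follows the plan gets the same single-opioid home regimen. A patient who empties the bottle and obtains nothing more has truly used 30 tablets, and nothing is lost. The error requires further supply, which the documents never mention. Eligibility also makes a separate home supply less likely, because Section 3.2 excludes chronic pain syndromes and pain medication taken for more than 3 months. Section 8.3 already allows a rank test, and Section 10.4 already names the medical record as a source.

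Much of this stands. It makes the bias conditional and its size unknown. It does not remove the mismatch: further supply is not ruled out either, and the plan as written could not show whether it had occurred.

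A reader might infer two stronger conclusions. One is that the heaviest users are in fact capped and that controls are hit harder. The documents do not support this: they give no expected home use by arm, and the block is stopped on postoperative day 3. The other is that a large share of the effect would be lost. An illustration with gamma-distributed use (coefficient of variation 0.8 to 1.0), a true one-third reduction and unlimited supply shrinks the mean difference by 5–13% at a control mean of 10 tablets and by 36–46% at 20. Every one of those inputs is invented, and unlimited supply is the very point at issue, so these figures are not an estimate for this trial.

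**Conclusion.** The point holds in conditional form. As written, the measurement is narrower than the endpoint: recorded use stops at 30 tablets, and any other oral opioid counts as zero. Bias in the comparison follows only if further opioid is obtained and the arms differ in how often. The size ranges from 0 tablets (extra use absent or equal) to 2 tablets per patient in the single assumed scenario; the documents do not allow a closer figure. Separately and without any assumption, the two statements of the counting window conflict and must be reconciled, since they set the period over which tablets are counted. This is a low-priority improvement to one secondary endpoint. The primary endpoint and the sample size do not change.

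**What to change.** - **Section 7.2.6:** on the same call, also record any refill and any other oral opioid taken since discharge, with drug, strength and number taken. Cross-check against prescriptions in the medical record. For withdrawn patients, record what was actually dispensed at discharge.
- **Sections 1.3 and 8.3:** define the endpoint as total oral opioid from all sources in a common unit, such as morphine equivalents, with the conversion factors fixed in advance. Use the Wilcoxon test already allowed if values are non-normal, for example piled up at 0 or at the full supply. Report by arm how many patients had no tablets left and how many obtained more, so that readers can see whether the ceiling mattered.
- **Sections 1.3, 7.2.6, 7.3 and 10.4:** state the timing of the contact in one consistent way.

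The cost is one added question on a planned call, one chart check per patient and a short text change. The call ends participation, so it is the last planned chance to ask. The downside is that refill use relies partly on patient recall, and the institution's record may miss prescriptions written elsewhere. No dose, prescription or clinical rule needs to change.
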